5. STATISTICAL CONSIDERATIONS

5.A Primary Analyses

Two primary (null) hypotheses have been defined for testing in ACT:

- H₁: there are no differences among the mean levels of VO₂max among persons randomized to the three groups of the clinical trial at 24 months post-randomization, and
- H₂: there are no differences among the mean levels of seven-day self-reported physical activity levels among persons randomized to the three groups of the clinical trial at 24 months post-randomization.

Each hypothesis will be tested according to the intention-to-treat philosophy (Friedman, 1985) in which all randomized participants will be grouped according to their intervention assignment at randomization, regardless of compliance. All primary comparisons will be two-sided (Fleiss, 1987). A Bonferroni adjustment for multiple comparisons will be used to control the Type I error across the two primary hypotheses: individually, each hypothesis will be tested at significance level 0.025. Separate hypothesis tests will be performed on women and men.

General linear models will be used to model the serial data collected on each primary outcome measure. Time since randomization will be grouped by targeted exams (i.e. 6 or 24 month) and parameterized as a fixed class effect. The primary hypotheses will be tested using linear contrasts for interactions between treatment assignment and the indicator variable for the 24 month exam. No *a priori* parametric structure will be assumed for serial correlation. The baseline level of the measure (i.e. VO₂max or seven-day physical activity recall) will be included as a covariate in models, as will terms for the stratification factors: clinical center and race (African-American, Hispanic, Other).

Extensive attempts are planned to promote the retention of ACT participants; however it is expected that not all randomized participants will be evaluated at 24 months. Including interim

data on VO₂max and seven-day physical activity in analyses testing the 24-month differences is expected to reduce the potential biases that may be associated with missing data. This approach allows all participants who have post-randomization measures to contribute to the analysis, and therefore does not exclude persons who are missing 24-month data.

Secondary analyses will be performed to explore the effect that assumptions about missing data have on trial results. Sensitivity analyses will be conducted in which analysis of results will be performed based on 1) assuming the missing data are missing at random, conditioned on the value of covariates and intermediate results, and 2) assuming that all the unobserved missing data in the intervention and control groups have the same distribution as the observed data in the control group. If these analyses indicate that the results differ substantially, depending on the assumptions one makes about the missing data mechanism, further analyses involving model-based alternatives to the planned primary analyses (e.g. Schluchter, 1992; Shih, 1992; Diggle and Kenward, 1994) and post-hoc stratification (e.g. D'Agostino, 1994) will be explored.

Based on analyses from the Stanford-Sunnyvale Health Improvement Project (SSHIP-I) trial, VO₂max measurements are anticipated to have a right-skewed distribution with the variance increasing with the mean; if this pattern emerges in ACT, a logarithmic transformation will be used, as in the sample size calculations presented below. Each of the three pairwise comparisons of the intervention groups will be tested using a Bonferroni-adjusted significance level of $\alpha=0.0083$ (0.025/3), as is specified in the sample size calculations.

5.B. Secondary Analyses

A series of publications based on the baseline data will be developed to provide the investigators with a first opportunity for a systematic exploration of the central databases; to assist in developing definitions of new variables for future analyses; to begin the development of scientific collaborations; and to cement the protocol for trial publications. Baseline analyses will include descriptions of recruitment, the baseline characteristics of the participants, and cross-sectional analyses of relationships among study variables.

Although the primary hypotheses only address 24-month change, it will be important to examine how the interventions may affect VO₂max and seven-day physical activity recall across the full 24 month period. Secondary analyses will be performed to track these measures across time using mixed effects analysis of covariance models to allow for both time-varying changes in covariates, and varying covariance structures (Laird and Ware, 1982; Jennrich and Schluchter, 1986; Diggle, 1988; Laird, 1992; Wolfinger, 1992).

Important secondary outcome measures include other measures of fitness and activity, factors related to cardiovascular risk (e.g. levels of lipoproteins, blood pressure, insulin, glucose, and fibrinogen), health related quality of life and cost. Methods similar to those described above will be used for continuous measures. For other types of response variables (categorical, ordered categorical, or counts), we will use the generalized estimating equation (GEE) approach to fit logistic or log-linear models that account for the dependency between repeated measures (Zeger and Liang, 1986; Liang and Zeger, 1986; Prentice, 1988; Zeger, 1988; Lipsitz, 1991; Liang, Zeger and Qaqish, 1992; Miller, 1993). Nonparametric approaches may also be adopted in some settings, as well (e.g. Zerbe and Walker, 1977; Raz, 1988).

A full description of compliance, predictors of compliance, and attrition comprise important

secondary analyses that will allow a more complete understanding of study results. Other important secondary analyses include descriptions of the effectiveness of interventions in pre-defined subgroups formed by race, age, and baseline measures of activity or fitness, body mass index, education, use of beta blockers, pre-existing co-morbid conditions, elevated ST segments, mood disorders, smoking, psychosocial factors and menopausal status. In some secondary analyses, data from women and men may be combined. Cross-sectional and longitudinal relationships among individual outcome measures, and between measures of adherence and outcomes, will also be described.

Importantly, the cross-sectional and longitudinal relationships between VO₂max and other measures of treadmill exercise performance and seven-day physical activity recall will be examined for internal consistency. The robustness of these relationships across study groups and participant subgroups will be assessed using regression analyses.

5.C. Sample Size Considerations

Sample size calculations for the ACT trial were based on recruitment of an equal number of participants to each of its three groups. The two primary outcomes in these calculations are logarithmic-transformed VO₂max measurements (unadjusted for weight) and total kilocalorie expenditure per kilogram body weight by seven-day physical activity recall, including light, moderate and heavy activities, but not including sleep. For each primary outcome, the hypotheses to be tested will investigate 24-month differences between all intervention groups; thus a total of six pairwise comparisons will be performed. Preliminary data used for estimating standard deviations of outcomes were obtained from the SSHIP-I trial run by investigators at Stanford University. Based on the SSHIP-I information, we estimated that the standard deviations of log transformed, 24-month VO₂max measurements adjusted for baseline measurements were 0.1214 for men and 0.1215 for women, respectively. Standard deviations for total kilocalorie expenditure were only available for 12 months of follow-up. The 12-month standard deviations of total kilocalorie expenditure were 2.0894 for men and 2.0206 for women, after adjustment for baseline measurements. Sample size calculations were performed separately for men and women.

To ensure an overall, two-sided, Type I error rate, α , of 0.05, each pairwise comparison will be performed at the 0.0083 level (0.05/6), thus using critical regions containing 0.00417 probability in each tail. Assuming equal variances of 24-month outcomes for all intervention groups, the general formula used to determine the appropriate sample size to detect a difference of δ with $1-\beta$ power is

$$N = \left(\frac{1}{r} \right) V \left(\frac{1}{P_1} + \frac{1}{P_2} \right) \frac{(Z_{1-\alpha/2/m} + Z_{1-\beta})^2}{\delta^2},$$

where r is the proportion of participants that will not be lost to follow-up prior to 24 months, V is the baseline adjusted variance of the outcome variable, P_1 and P_2 are the proportion of subjects in the groups being compared, m is the number of trial groups times the number of primary outcomes, and $Z_{1-\alpha/2/m}$ and $Z_{1-\beta}$ are percentiles from a standard normal distribution. For the calculations reported below, we assume 20% loss to follow-up ($r = 0.8$) and have allowed equal numbers in each group. $Z_{1-\alpha/2/6} = Z_{0.00417} = 2.64$ and, for 90% power, $Z_{1-0.1} = 1.282$.

The sample size of the trial is based on being able to detect a 7% difference in VO_{2max} and a $1.1 \text{ kcal} \cdot \text{kg}^{-1} \cdot \text{day}^{-1}$ difference in total energy expenditure with 90% power. The 7% difference would equal a difference of $2000 \text{ ml} \cdot \text{min}^{-1}$ versus $1869 \text{ ml} \cdot \text{min}^{-1}$. The goal of the intervention groups is to target an increase in energy expenditure equal to approximately $2 \text{ kcal} \cdot \text{kg}^{-1} \cdot \text{day}^{-1}$. The trial is designed to detect an intervention that would obtain this increase on some but not all participants. It is anticipated that a successful intervention would cause some individuals to exceed these goals and some would not improve from baseline. The trial was designed to be able to detect an intervention that results in the following distribution of effects:

- No increase in 25% of subjects
- 1 $\text{kcal} \cdot \text{kg}^{-1} \cdot \text{day}^{-1}$ increase in 25% of participants
- 2 $\text{kcal} \cdot \text{kg}^{-1} \cdot \text{day}^{-1}$ increase in 45% of participants
- 3 $\text{kcal} \cdot \text{kg}^{-1} \cdot \text{day}^{-1}$ increase in 5% of participants

for an average increase of $1.3 \text{ kcal} \cdot \text{kg}^{-1} \cdot \text{day}^{-1}$. The control subjects are assumed to have a distribution of:

- 1 $\text{kcal} \cdot \text{kg}^{-1} \cdot \text{day}^{-1}$ decrease in 10% of control participants
- 0 $\text{kcal} \cdot \text{kg}^{-1} \cdot \text{day}^{-1}$ change in 85% of control participants
- 1 $\text{kcal} \cdot \text{kg}^{-1} \cdot \text{day}^{-1}$ increase in 10% of control participants
- 2 $\text{kcal} \cdot \text{kg}^{-1} \cdot \text{day}^{-1}$ increase in 5% of control participants

for an average increase of $0.2 \text{ kcal} \cdot \text{kg}^{-1} \cdot \text{day}^{-1}$. Based on the above assumptions, it will be necessary to randomize 393 women and 417 men to have 90% power to detect a $1.1 \text{ kcal} \cdot \text{kg}^{-1} \cdot \text{day}^{-1}$ difference in total energy expenditure. These sample sizes will also allow ACT to detect a 7% change in VO_{2max} with approximately 91% power in women and 93% power in men.

5.D. Interim Analysis and Early Stopping

Major interim statistical reports will be prepared biannually for the Steering Committee so as to keep investigators blinded to outcomes. Statistical reports of unblinded results will be circulated to the Data and Safety Monitoring Board and the Project Office. In addition to data that will be reported more frequently (e.g., biweekly recruitment reports and other special reports), these major reports will be developed to provide a comprehensive picture of the status of the study.

Monitoring of clinical trials is generally required on ethical grounds, although it can be further justified by a number of practical considerations. Once the scientific and medical questions of primary interest have been answered, stopping the trial avoids expending additional time, money and effort (Friedman, 1985). The primary outcomes of ACT center on the effect of interventions at 24 months. Recruitment will be completed by the time appreciable information has been collected on these outcomes, so the advantages of early stopping rules based on the primary 24-month outcome measures are considered unprofitable to use in formal stopping rules for ACT. Instead, the Data and Safety Monitoring Board for ACT will assess the need for early stopping based on safety or on the likelihood that a statistically significant difference between treatment groups by the end of the study is improbable based on 6-month data. Group sequential testing using a Type I error spending function for multiple endpoints and longitudinal measures of effectiveness (Reboussin, 1992) will be recommended.

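### The flat 0.0083 level for all three pairwise tests in section 5.A is valid, but a three-group step-down gains power at the same error rate with no extra participants

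*Protocol*

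**What the plan says.** Protocol section 5.A sets two primary null hypotheses at 24 months, one for VO2max and one for the seven-day activity recall. Each is worded across all three groups; for the recall, "there are no differences among the mean levels of seven-day self-reported physical activity levels among persons randomized to the three groups". The 0.05 is split by Bonferroni over the two outcomes: "individually, each hypothesis will be tested at significance level 0.025". Tests are two-sided, and "Separate hypothesis tests will be performed on women and men". The method is given as follows: "The primary hypotheses will be tested using linear contrasts for interactions between treatment assignment and the indicator variable for the 24 month exam".

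The same section later fixes the pairwise level: "Each of the three pairwise comparisons of the intervention groups will be tested using a Bonferroni-adjusted significance level of" 0.0083, shown there as 0.025/3. Section 5.C reaches the same level by counting three pairs for each of two outcomes ("thus a total of six pairwise comparisons will be performed") and dividing 0.05 by 6. It derives the sample size from that level. The protocol gives no step-down rule. The primary objectives in section 1.B are pairwise: each regimen against Standard Care, and the two regimens against each other.

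**The concern.** A flat 0.025/3 treats the three pairwise nulls as if any combination of them could be true. That is not so for three group means. If two of the equalities A = B, A = C and B = C hold, the third holds as well, so the number of true nulls is 0, 1 or 3 and never 2. After one correct rejection, at most one false rejection remains to guard against, and dividing 0.025 by three for the remaining tests gives up power for no gain in error control.

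The loss falls on the trial's own questions. The objectives ask for B against A, C against A and C against B. The present rule costs most when more than one of these is to be shown, or when the less resource-intensive regimen B has a smaller effect than C.

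There is also a minor point of wording. H1 and H2 are phrased as three-group nulls at 0.025, and no sentence in 5.A says outright that the pairwise tests are what decides them.

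**Working it through.** **Inputs (section 5.C).** Baseline-adjusted SD of energy expenditure: 2.0894 in men and 2.0206 in women (12-month values). Design difference 1.1 kcal/kg/day, 90% power, 20% loss (r = 0.8), equal allocation, m = 6.

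**1. The alpha chain.** 0.05/2 = 0.025, and 0.025/3 = 0.05/6 = 0.00833, with two-sided z = 2.638 (protocol: 2.64). Sections 5.A and 5.C agree.

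**2. The plan's own sample size.** N = (1/r) × V × (1/P1 + 1/P2) × (z_alpha + z_beta)² / δ², where 1/P1 + 1/P2 = 6 and (2.638 + 1.282)² ≈ 15.37.

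- Men: (1/0.8) × 2.0894² × 6 × 15.37 / 1.1² ≈ 415.8, or 417 when rounded up per arm (stated 417).
- Women: (1/0.8) × 2.0206² × 6 × 15.37 / 1.1² ≈ 388.8, or 390 when rounded up per arm (stated 393).

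At level 0.025 the same formula gives 335.8 and 314.1, so the stated numbers belong to the pairwise tests at 0.0083. VO2max power at the stated N comes to 0.935 in men and 0.918 in women (stated 93% and 91%).

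**3. Power per comparison as planned.** Evaluable per arm: 417 × 0.8/3 = 111.2 men and 393 × 0.8/3 = 104.8 women. The standard error of a difference is SD × √(2/n), which is 0.280 in men and 0.279 in women. So 1.1/SE − 2.638 is about 1.29 and 1.30, giving power of 0.901 and 0.904. The planned 90% is confirmed.

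**4. Error rate of the step-down.** Rule: smallest p at 0.025/3; if rejected, the other two at 0.025 each.

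- All three nulls true: any false rejection needs the smallest p to be at or below 0.025/3. The probability is at most 3 × 0.025/3 = 0.025.
- Exactly one null true: it is rejected only if its own p is at or below 0.025. The probability is at most 0.025.
- None true: no false rejection is possible.

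The per-outcome familywise error is therefore at most 0.025, and two outcomes give at most 0.05 within each sex, as now. In the simulation below, the largest rate observed was 0.025.

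**5. Nothing is lost.** If any p is at or below 0.0083, the smallest p is too, so the first step rejects. Every other p at or below 0.0083 then also passes 0.025.

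**6. What is gained.** Simulation of 1,000,000 three-arm trials per scenario for energy expenditure at the planned evaluable numbers. Effects are gains over A. Only the 1.1 difference is the protocol's; the other values are assumptions.

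| Scenario | Quantity | Flat 0.0083 (men / women) | Step-down (men / women) |
|---|---|---|---|
| B 1.1, C 1.1 | each regimen vs A | 0.90 / 0.90 | 0.94 / 0.94 |
| | both vs A | 0.834 / 0.837 | 0.911 / 0.915 |
| | at least one rejection | 0.968 / 0.969 | 0.968 / 0.969 |
| B 0.8, C 1.1 | B vs A | 0.585 / 0.590 | 0.714 / 0.718 |
| B 0.55, C 1.1 | B vs A | 0.250 / 0.252 | 0.385 / 0.388 |
| | C vs B | 0.249 / 0.251 | 0.384 / 0.387 |
| B 0.7, C 0.7 | each regimen vs A | 0.44 / 0.45 | 0.51 / 0.52 |
| | both vs A | 0.279 / 0.283 | 0.412 / 0.416 |

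For comparison, Holm's method in women at B = C = 1.1 gives 0.921 per comparison and 0.872 for both. It sits between the two because it does not use the link among the three nulls.

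**The case against.** The strongest reply is that nothing here is wrong. Single-step Bonferroni controls the error, the trial was sized for it, and the planned 90% per comparison is met. Section 5.C plans power for a difference of 1.1; it sets no target for declaring both regimens at once, so the 83-84% misses nothing that was promised. At the design effect the gain per comparison is about 4 points, and the chance of at least one rejection does not move. The larger gains depend on assumed effects. Refinements of this kind are often placed in an analysis plan, which was not at hand. All of this stands, and it is why the point is an improvement. It does not remove the case for the change, because 5.A itself fixes the flat level and the replacement is never less powerful.

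A reader might infer something stronger: that 5.A sets up two competing decision rules, an overall three-group test at 0.025 and pairwise tests at 0.0083, with nothing to say which decides. The protocol does not support that. It names no overall statistic, and the linear contrasts it describes fit pairwise tests. The figures read naturally as one budget, 0.05 to 0.025 per outcome to 0.0083 per pair. Section 5.C ties the hypotheses to six pairwise comparisons and secures the overall 0.05 through those alone.

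Even if a separate 2-df test at 0.025 were run, it would rarely disagree with the pairs. Under the global null it would do so in about 0.6% of trials (0.40% overall test only, 0.18% a pair only). With both regimens at 1.1 the figure is under 1%, and with both at an assumed 0.7 it is about 4.3%. Rejecting on either would give 0.027 per outcome instead of 0.025, so this is not material inflation.

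**Conclusion.** The point holds as a cheap improvement. The flat 0.0083 is a valid rule, consistent with the sample size, but with three groups it gives up power that can be recovered at the same 0.025 per outcome. At the protocol's design effect in both regimens, the gain is from 90% to 94% per comparison with A, and from 83-84% to about 91% for showing both. If B gains an assumed 0.55 and C 1.1, power for B vs A and for C vs B rises from 25% to 38-39%. The chance of at least one rejection is unchanged.

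The error bound needs only valid pairwise p-values and three groups. The power figures also rest on normal theory, the protocol's SDs, equal arms and 20% loss. They were computed for energy expenditure; VO2max was not simulated under the step-down. The wording of H1 and H2 as three-group nulls at 0.025 is a minor ambiguity that one sentence settles.

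**What to change.** In section 5.A, replace the flat 0.0083 for each pairwise comparison with a Shaffer step-down within each outcome and sex: test the smallest of the three p-values at 0.0083 and, if it is rejected, test the other two at 0.025 each; otherwise stop. Where H1 and H2 are stated, add a sentence saying that these pairwise tests decide them, as section 5.C already implies. Keep 0.0083 in section 5.C as the conservative planning basis, so that 417 and 393 do not change.

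The cost is a wording change before unblinding, with no added participants, visits or data. The one drawback is that simultaneous confidence intervals matching the step-down tests are less simple. Bonferroni intervals at 1 − 0.0083 = 99.17% can still be reported, with a note that a comparison rejected at the second step may have such an interval that includes zero. If the analysis plan already specifies a step-down, only the text of 5.A needs to be aligned with it.

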Patterns of physical activity vary with demographic characteristics (Pate, 1995). Men are more likely than women to engage in physical activity (Dishman, 1991) and the total amount of time spent engaging in physical activity declines with age (Caspersen, 1992). African-Americans and other ethnic minority populations are somewhat less active than White Americans and this disparity is more pronounced for women (Caspersen, 1992). People of higher socioeconomic status participate in more leisure time physical activity than those of lower socioeconomic status. Some of the racial and ethnic differences in physical activity may reflect differences in socioeconomic status.

Characteristics of the individual and of the type of activity are related to participation in physical activity. Lack of time and concerns about injury are common reasons people do not participate in regular physical activity (Martin, 1982). Persons who are obese are often inactive (Bouchard, 1993). An intention to exercise and awareness of the benefits of exercise are weakly related to participation in physical activity; on the other hand, confidence in one's ability to be physically active and to overcome barriers to inactivity and enjoyment of activity are strongly related to participation (Sallis, 1989). Low to moderate intensity activities are more likely to be continued than high intensity activities. Self-regulatory skills, social support, and conducive environments are also associated with increased physical activity.

Physicians and other health care providers have been identified as important avenues for reaching sedentary individuals and encouraging increases in their physical activity. Healthy People 2000 includes an objective on physician counseling for physical activity (DHHS, 1991), and the U.S. Preventive Services Task Force recommends counseling by physicians for all sedentary patients (Harris, 1989). Despite the recommendations, data show that relatively few primary care physicians routinely inquire about their patients' exercise habits and attempt to intervene in the sedentary (Williford, 1992; Taylor, 1983). Although physicians express an interest in physical activity counseling, they often lack the time to enter into discussions about exercise with their patients and may not feel they have the skills to provide physical activity counseling.

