2. TRIAL DESIGN AND METHODS

2.A. Study Design

ACT is a multicenter, randomized controlled trial designed to test the effects of two primary-care practice-based physical activity interventions on the adoption and maintenance of physical activity in sedentary participants. The two interventions (B and C) will be compared to a Standard Care control group (Group A) and to each other. The primary outcomes of physical activity ($\text{kcal} \cdot \text{kg}^{-1} \cdot \text{day}^{-1}$) and VO_2max ($\text{L} \cdot \text{min}^{-1}$) will be analyzed separately for men and women. Participants will be randomly allocated and stratified by gender, race, and clinical site.

Eight hundred ten participants from three clinical centers (CCs) will each be randomly assigned to one of three study groups: A- Standard Care Control; B- Staff-Assistance Intervention; C- Staff-Counseling Intervention. In all three conditions, participants will receive physician advice to increase their physical activity and will be provided with current recommendations for physical activity (the CDC/ACSM recommendation of accumulating 30 minutes of moderate physical activity on most days of the week and the ACSM prescription for cardiorespiratory endurance). In Interventions B and C, behavior-change programs will be implemented that have been designed to help participants increase their physical activity in order to meet the recommendations. The major difference between these two interventions is the degree of resources and staff burden required. The interventions will be delivered by health educators throughout the two-year intervention period.

2.B. Study Population

Inclusion Criteria

The study population for ACT will consist of participants who are:

- community-dwelling men and women;
- 35-75 years of age;
- receiving primary care from a participating study physician;
- scheduled to see a study physician during the recruitment phase of the study;
- exhibiting a sedentary lifestyle, defined as energy expenditure of $\leq 35 \text{ kcal} \cdot \text{kg}^{-1} \cdot \text{day}^{-1}$ measured by 7-day PAR;
- willing and able to participate in all aspects of the trial;
- in stable health;
- independent in activities of daily living;
- able to alter physical activity in accordance with the intervention program;
- if on medication for chronic disease, on a stable dose for the last 3 months; and
- willing and able to give informed consent.

Exclusion Criteria

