The randomization process will be stratified by Clinical Center, race and gender to ensure an even distribution of the number of participants per group for males and females and for each of the three races within each CC. Eighteen computerized randomization lists (a sequence of treatment assignments of about 300% more than the expected enrollment in a given clinic) will be generated using permuted block randomization with random block size.

2.F. Participant retention

A systematic effort will be made to maximize retention of subjects in the trial. Participants will be given a clear, detailed explanation of the procedures and time commitments of the trial prior to randomization. Randomized participants will receive written reminders of data collection appointments two weeks prior to the scheduled appointment. Participants who cancel appointments or who do not show up for data collection appointments will be called and the appointment rescheduled. Participants will be offered free transportation to data collection visits. Participants will receive periodic information about the progress of the study and individual communications such as birthday cards. Each CC will develop an incentive program for participants who complete data collection visits by awarding token prizes and other incentives, such as gift certificates.

2.G. Schedule of Follow-up Visits

Major data collection visits will occur at baseline and at 6 and 24 months after randomization. At these clinic visits, data to determine primary and secondary outcomes will be obtained as well as data on adherence to the physical activity interventions and adverse events. (See Table 1). A 12-month phone contact will be utilized to collect data on 7-day Physical Activity Recall.

2.H. Study Timetable

ACT consists of three phases:

Phase I represents the planning phase for ACT, which will run from September 30, 1994 until September 29, 1995. During these 12 months, the ACT Steering Committee will meet six times. The four subcommittees to the Steering Committee (Recruitment/Eligibility, Design and Analysis,

Measurement, and Intervention), will also meet at these times, and will also have regular conference calls to develop recommendations to the Steering Committee concerning study endpoints, the target population, recruitment and screening strategies, statistical issues, forms development, variables to be measured and study interventions.

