Shih WJ. On informative and random drop-outs in longitudinal studies. *Biometrics* 1992;48:970-972.

Speilberger CD. *Manual for the State-Trait Anxiety Inventory (Form Y)*. Palo Alto, CA: Consulting Psychologists Press, 1983.

U.S. Department of Health and Human Services. *Healthy People 2000; National Health Promotion and Disease Prevention Objectives*. DHHS Pub. No. (PHS) 1991;91-50212.

Wolfinger R. A tutorial on mixed models. Cary, NC: SAS Institute Inc, 1992.

**TABLE 1.
SCHEDULE OF ACTIVITIES**

	Clinic Chart Review	Phone Prescreen	SV0 Orient. Visit	SV1	SV2	Initial MD Visit	6mo FU Visit	12mo Phone Call	18 Month Ph Mail	24mo(a) FU Visit	24mo(b) FU Visit
Eligibility and Recruitment/Tracking	X										
Age and other eligibility data											
Telephone recruitment		X									
Informed Consent			X								
Demographics and Medical Hx and health habits			X								
7-Day Physical Activity Recall			X				X	X		X	X
Contact information; distribute at SV0				X							
Medications Inventory				X			X			X	
Physical exam				X							
Randomization						X					
Primary/Secondary Outcomes											

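### The primary models leave out age, which is known for every participant and is not a randomization stratum, so precision that may be available at no cost is not fully used

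*Protocol*

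**What the plan says.** Protocol 5.A fits general linear models to the 6- and 24-month data, separately for men and women, and names the covariates. First: "The baseline level of the measure (i.e. VO₂max or seven-day physical activity recall) will be included as a covariate in models". Then: "as will terms for the stratification factors: clinical center and race (African-American, Hispanic, Other". These match the design within each sex, since under 2.E "The randomization process will be stratified by Clinical Center, race and gender".

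Age appears elsewhere:
- 2.B sets eligibility at "35-75 years of age".
- Table 1 lists "Age and other eligibility data" as the first item collected.
- 1.A states that "the total amount of time spent engaging in physical activity declines with age".
- Secondary objective f and 5.B use age as a subgroup factor; 5.B refers to "pre-defined subgroups formed by race, age, and baseline measures of activity or fitness".

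On missing data, 5.A brings the 6-month results into the 24-month analysis and plans two sensitivity analyses. One proceeds by "assuming the missing data are missing at random, conditioned on the value of covariates and intermediate results"; the covariates meant there are not listed.

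**The concern.** Adjusting for a baseline variable that predicts the outcome reduces residual variance and so narrows the treatment contrasts. Age is a natural candidate: it covers a 40-year range, is complete, and is linked to activity by the protocol itself. Stratification does not balance it, and the analyses are split by sex, leaving about 105 to 111 expected completers per arm.

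The baseline outcome carries some of the age information but need not carry all of it. Baseline PAR is a self-report measure, which 1.B says may be imprecise, and entry is capped at 35 kcal/kg/day. For VO2max, one baseline value may not capture differences by age in change over the next two years.

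At stake is a modest amount of precision. A secondary benefit is possible in the missing-data analyses: 20% loss is planned, and a missing-at-random assumption is somewhat more plausible when it conditions on a variable that may relate both to loss and to outcome.

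**Working it through.** **Inputs (Protocol 5.C).** Two-sided alpha per pairwise test 0.05/6 = 0.0083; z = 2.64 (2.638 unrounded) and 1.282; retention r = 0.8; three equal groups. Baseline-adjusted SDs: PAR 2.0894 (men) and 2.0206 (women), from 12-month data; log VO2max 0.1214 and 0.1215. Targets: 1.1 kcal/kg/day and 7%, taken as ln 1.07 = 0.0677. Planned N: 417 men, 393 women.

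**Step 1: reproduce the plan.** With P1 = P2 = 1/3, the 5.C formula is N = (1/0.8) × SD² × 6 × (2.64 + 1.282)² / 1.1².
- Men: 416.2, or 417 when rounded up per arm (planned 417).
- Women: 389.3, or 390 when rounded up per arm (planned 393, about 1% higher).

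Expected completers per arm are 0.8 × 417/3 = 111.2 men and 0.8 × 393/3 = 104.8 women. Power = Φ(δ / (SD × √(2/n)) − 2.638).
- PAR, men: SE = 2.0894 × √(2/111.2) = 0.280; 1.1/0.280 − 2.638 = 1.287; power 90.1%.
- PAR, women: SE = 2.0206 × √(2/104.8) = 0.279; 1.1/0.279 − 2.638 = 1.302; power 90.4%.
- VO2max: 93.5% in men and 91.8% in women (plan: about 93% and 91%).

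The plan's figures hold, and they rest on SDs adjusted for baseline only. Nothing in them relies on age.

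**Step 2: add age.** Let R² be the share of the baseline-adjusted variance explained by age, so that SD becomes SD × √(1 − R²). The documents give no value for R²; the range below is an assumption.

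| Assumed R² | SE reduction | PAR power, men | PAR power, women | VO2max power, men | VO2max power, women |
|---|---|---|---|---|---|
| 0 | none | 90.1% | 90.4% | 93.5% | 91.8% |
| 0.01 | 0.5% | 90.4% | 90.7% | 93.8% | 92.1% |
| 0.02 | 1.0% | 90.8% | 91.0% | 94.1% | 92.4% |
| 0.05 | 2.5% | 91.8% | 92.0% | 94.8% | 93.3% |
| 0.10 | 5.1% | 93.3% | 93.5% | 95.9% | 94.6% |

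For PAR, the N needed for 90% power would fall from 416 to between 412 and 374 in men, and from 389 to between 385 and 350 in women.

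**Step 3: scale of any dropout effect.** Suppose an age SD of 10 years, a partial correlation of age with outcome of 0.1 to 0.3, and a difference of 1 to 3 years in completers' mean age between arms (all assumptions). The shift in the contrast is correlation × outcome SD × (difference/10). For PAR, with an SD of about 2.05, this runs from 0.1 × 2.05 × 0.1 = 0.02 to 0.3 × 2.05 × 0.3 = 0.18 kcal/kg/day, against a target of 1.1. For log VO2max it runs from 0.001 to 0.011, against 0.068.

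**The case against.** The strongest reply is that nothing here is wrong. Adjusting for the baseline outcome and the stratification factors is a standard, acceptable model. Planned power is met without age. 5.A says its listed terms will be included but does not say that no others may be, and further covariates are often settled in the analysis plan, which is not shown. The statement in 1.A concerns a general relation of age with activity; what matters is the relation left after baseline adjustment, within one sex, among people selected as sedentary, and the documents do not give it. The R² range is therefore unanchored. BMI, smoking or beta-blocker use could be proposed on similar grounds. All of this stands, and it limits the point to an optional improvement. What remains is that 5.A does name a covariate set, and that age is complete and specifically linked to activity in the protocol. Power for PAR also has little margin above 90% and rests on 12-month SDs. If the 24-month SD in men were 5% larger (an assumption), power would be about 86.4%; age at R² = 5% would bring it to about 88.4%.

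Three stronger readings are tempting, and the documents support none of them:
- **That omitting age gives up protection against dropout bias.** The 6-month outcomes are in the primary model, participants without 24-month data are retained, and sensitivity analyses follow, with further modelling if results differ. Age-related loss would bias the contrast only if it differed by arm (or age modified the effect) and age also predicted the 24-month outcome beyond the baseline and 6-month values.
- **That the missing-at-random analysis conditions solely on the primary model's covariates.** The text says covariates without listing them, and age could be among them.
- **That baseline PAR retains little of the age gradient.** No figure supports this, and the recall is given twice at baseline to improve precision.

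**Conclusion.** The point holds as a minor improvement, not as an error. The primary models are valid, contradict nothing in the protocol, and every stated sample size and power figure stands. Age is left out although it is complete, wide-ranging, unstratified and described as related to activity, so precision that may be available is not fully used.

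Under the assumed R² of 1% to 10%, the gain in PAR power is about 0.3 to 3.2 points in either sex; at 1% to 2% it is under one point and may be negligible. Any benefit for the missing-data assumption is a matter of plausibility and cannot be quantified from the documents.

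**What to change.** In 5.A, prespecify baseline age, as a continuous term, as an additional covariate in both primary models, in men and in women. Name it also among the covariates of the missing-at-random sensitivity analysis. If an analysis plan already includes age, align the two texts.

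The cost is a few words, one degree of freedom per model and no new data. The change should be made before unblinded outcome data are seen, because a covariate added afterwards would invite criticism. A main-effect term does not address effect modification by age; the planned subgroup analyses remain the place for that.
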